Assess the effects of the intervention strategies when delivered “all-in” versus “add-in” by measuring the following outcomes.

- Dispersion: Via EHR extraction- Proportion of children over 2 months of age who have NBS/SCT newly documented (as above).
- Knowledge: Caregiver survey- Proportion of caregivers who accurately reported their child's NBS result.
- Inequities in documentation: Via chart review. Demographic data for each infant: primary care site, sex, race, ethnicity, and insurance type.
- Satisfaction: Caregiver survey.

INVESTIGATIONAL PLAN: Overview

General Schema of Study Design

A two-arm, randomized, interrupted time series design will compare an “all-in” and “add-in” approach. In the “all-in” arm, participants receive all toolkit components at once. In the “add-in” arm, participants will have “multiple interruptions” with sequential addition of components in 6 week increments (**Figure – replace 3 month label with 6 week label**). This will allow for exploration of the added benefit of certain components as compared to the whole toolkit.

Toolkit Components:

- 1) Intervention A: EHR “nudge” within the birth history and/or well-child progress note template
- 2) Intervention B: “lunch-and-learn” sessions (in person or pre-recorded per office preference)
- 3) Intervention C: written educational materials (i.e. post cards, poster, PDF files) to alert PCPs to the importance of SCT documentation and “talking points” to facilitate disclosure;

Duration of Study Participation

Duration of study participation for a site will last a total of approximately 5 months. During the 5 months, PCPs will participate in 4 surveys (15 minutes each) and 1 qualitative interview (30 minutes). Study duration of caregivers will be for survey completion (5-10 minutes).

Total Number of Study Sites/Total Number of Subjects Projected

- 1) Sites: At least 2 sites per arm of the study with at least 10 PCPs in each arm are required.
- 2) PCPs: All PCPs from a given office will be eligible for participation. This will result in at least 20 Nemours PCPs at 4 or more office locations in the Delaware Valley. PCP offices will be purposively chosen to include a wide racial distribution within their patients.
- 3) Caregivers: 500 caregivers of infants with SCT or a normal NBS who are cared for within the specified office location.

Study Population

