PCP Implementation Surveys: PCPs will receive surveys by email (through REDCap) every 6 weeks. Survey is expected to take 15 minutes to complete. For PCPs in the “all-in” arm, the first survey will be sent prior to the intervention “roll-out” and every 6 weeks after that. For PCPs in the “add-in” arm, the first survey will be sent prior to intervention A “roll-out”, intervention B “roll-out”, intervention C “roll-out”, and then 6 weeks after. The survey is created specifically for this study and focused on the acceptability of using the intervention component, feasibility of using the intervention component, the opportunity costs of using the intervention component (the time it takes to use the intervention, the perceived effect on other discussion topics with well child visits), and the intention and confidence (i.e. self-efficacy) to document and discuss NBS and SCT results.

PCP Qualitative Interviews: At completion of the Intervention period, PCP participants will be contacted to schedule the qualitative interview. Interviews will be expected to last ~30 minutes. Interviews will be completed over the telephone or using a video conferencing platform. If video conferencing is used, participants will be instructed to keep their camera turned off, so their image will not be recorded. The participant will be notified verbally when the recording has started and when it has stopped.

The qualitative interviews will assess their experience with the components and intention to document and disclose NBS/SCT results in the future.

Infant Identification:

Infants seen at a participating site during the retrospective and intervention period for a well child visit before 2 months of age will be identified through EHR data extraction on a rolling basis (i.e. once a month during the trial) based on ICD10 code for a new patient/well child exam (ICD 10: Z00.110, Z00.111, Z00.121, Z00.129, Z00.00, Z00.01 or CPT: 99381, 99382, 99383, 99384, 99385, 99391, 99392, 99393, 99394, 99395).

Documentation and Discussion of NBS/SCT results for all infants identified: via chart review. For each infant identified, the following data will be collected via EHR extraction and manual chart review:

- Email
- Preferred language
- MRN (to facilitate manual chart review)
- Gender
- Race, ethnicity
- Insurance
- Zipcode (to assess Childhood Opportunity Index)
- Phase of study they were first seen for a WCC (retrospective, “all-in” A/B/C, Intervention A, Intervention B, Intervention C)

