- Presence/absence of NBS
- Result of hemoglobinopathy NBS
- Presence/absence of NBS result documented in 1) problem list, 2) medical history, 3) progress notes
- Presence/absence of a disclosure conversation about NBS result in progress notes (including topics discussed: inheritance patterns, medical implications, reproductive implications, hematology/genetics consultation)
- Presence/absence of NBS results in After Visit Summary communication

Caregiver Survey from retrospective period:

Caregivers of three groups of infants will be surveyed if they are identified as speaking English (through EHR demographic data) and with an email address in the EHR:

- Group 1: All infants with SCT seen before 2 months of age within the 6 month retrospective period
- Group 2: All infants identified as Black or Hispanic seen before 2 months of age within the 6 month retrospective period

- Group 3: Infants seen before 2 months of age within the 3 month retrospective period and not included in group 1 or 2

Caregiver Survey during Intervention Period:

Caregivers from the participating office locations of three groups of infants will be surveyed if they are identified as speaking English (through EHR demographic data) and with an email address in the EHR:

- Group 1: All infants with SCT
- Group 2: All infants identified as Black or Hispanic
- Group 3: Infants seen in the first half of the month and not included in group 1 or 2

Caregivers will receive a survey at 2 and 6 months of age (+/- 1 month) delivered by email (through REDCap). Survey is expected to take less than 10 minutes to complete. Consent and survey responses will be obtained electronically. The survey will inquire about results of the NBS, preferences for information receipt, and satisfaction with well child visit.

Recruitment of Participants

- **See site selection under Study Procedures**

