We are requesting to waive a signature for consent, as the participants will be asked to document consent/assent via REDCap survey, and reaffirm consent/assent verbally prior to the qualitative interview. The surveys and qualitative interview presents no more than minimal risk to the participants. Additionally, we are not asking for any additional personal health information or identifiers apart from Greenphire information. The consent document would be the only other document connecting the survey responses and the PCP. The participants will be provided with an information sheet in recruitment emails and prior to starting the REDCap survey.

We are asking for a waiver of HIPAA authorization. The survey study involves no more than minimal risk to the participant. Additionally, the HIPAA form would be the only other document connecting survey response and the participant. Because we want the participants to be as honest as possible, we do not want the participant to feel that we can connect them to their responses and that connection could include the HIPAA documentation.

PHI will be used 1) to ensure eligibility of participants; 2) to contact for recruitment; and 3) to appropriately describe our sample. We will collect identifiable information (i.e. DOB and address) for those who receive a gift card to process study payment through Greenphire. This data will not be provided to or used for anything aside from payment. As this study will be conducted entirely remotely, it cannot be conducted without access to and use of PHI such as

Subject Completion/Withdrawal

contact information.

Subjects may withdraw from the study at any time without prejudice to their care or employment. The PI may withdraw a participant from the study if it is learned that they did not fulfill eligibility criteria. It will be documented whether or not each subject completes the study.

STATISTICAL CONSIDERATIONS

Evaluation of the Toolkit will focus on Proctor's framework of IS outcomes:⁴⁷

Primary Endpoint

- Penetration (via interrupted time series): via EHR extraction. Rate of scanned NBS results available in the EHR. Rate of documentation and disclosure of NBS and SCT result at < 2 months of age in each of the following: the problem list, the medical history section, and progress note. Evaluate monthly: retrospectively (pre intervention) and prospectively (post intervention).

Secondary Endpoint

- Acceptability: via PCP survey for each toolkit component.

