- Feasibility: Percent of PCPs who use individual toolkit components.
- Adoption/Self-efficacy: PCP survey. Intention and confidence to document/discuss NBS/SCT result.
- Cost: PCP survey: Perceived time (in mins) to document and discuss NBS/SCT result, effect on other discussion topics during the visits.
- Dispersion: Via EHR extraction- Proportion of children over 2 months of age who have NBS/SCT newly documented (as above).
- Knowledge: Caregiver survey- Proportion of caregivers who accurately reported their child's NBS result.
- Inequities in documentation: Via chart review. Demographic data for each infant: primary care site, sex, race, ethnicity, and insurance type.
- Satisfaction: Caregiver survey.

Statistical Methods

Unit of analysis will be the individual PCP (i.e. pre/post) and by trial arm with the primary end point being the rate of documentation and disclosure of NBS and SCT (penetration).

Data will be summarized in numeric and graphic forms. Mean and standard deviation or median and interquartile range will be used for summarizing numerical variables and frequencies and percentages will be used for categorical variables. PCP's EHR documentation and disclosure of newborn screen (NBS) and sickle cell trait (SCT) carrier results will be presented by pre-post intervention as well as by intervention groups. The primary end point of the study is to compare the proportion of PCP's/ EHR documentation and disclosure of NBS and SCT between pre- and post- intervention periods.

Generalized linear mixed effects model will be used for the analysis of the primary end-point. Odds ratio with confidence interval will be provided for the documentation and disclosure. Generalized linear mixed effects model will also be used to compare the proportion of post-intervention documentation and disclosure over time (monthly) between two intervention groups. Mean score of acceptability for each intervention (A, B, C) as well as mean total score for all three interventions will be compared between two intervention groups. Similarly, other survey results such as Self-Efficacy of PCP to document NBS and time cost will be compared between two intervention groups. Also, dispersion, caregiver knowledge and caregiver satisfaction will be

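### The all-in versus add-in comparison of documentation is specified on post-intervention data alone and names no baseline term, although the same clinics' pre-intervention rates are collected

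*Combined protocol and SAP*

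**What the plan says.** The combined protocol and SAP describes the design under General Schema of Study Design: "A two-arm, randomized, interrupted time series design will compare an “all-in” and “add-in” approach". The penetration endpoint (documentation and disclosure of newborn screen and sickle cell trait results) carries the instruction "Evaluate monthly: retrospectively (pre intervention) and prospectively (post intervention". Under Infant Identification, the data cover "Infants seen at a participating site during the retrospective and intervention period for a well child visit before 2 months of age".

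Statistical Methods then gives two models for this endpoint.
- The primary one compares "EHR documentation and disclosure of NBS and SCT between pre- and post- intervention periods"; arm is not mentioned.
- The second, the only model stated for the randomised comparison, is to "compare the proportion of post-intervention documentation and disclosure over time (monthly) between two intervention groups"; the pre-period is not mentioned.

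Pre-period data and arm meet only in a descriptive sentence, where results are "presented by pre-post intervention as well as by intervention groups".

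For the caregiver outcomes the text is "Also, dispersion, caregiver knowledge and caregiver satisfaction will be" compared between the two groups. A retrospective caregiver survey is planned at the same offices ("Caregivers of three groups of infants will be surveyed if they are identified as speaking English"), but no analysis is named that uses it.

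The minimum is two sites and 10 PCPs per arm. Sites are randomised within dyads or triads formed on patients' racial demographics. Random effects for PCP within clinic are to be used as needed.

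**The concern.** With about four clinics, randomisation cannot be relied on to give the arms similar starting rates, and the matching variable is not the outcome. A post-only contrast therefore adds whatever stable difference exists between the arms' clinics and PCPs to the effect of delivery mode. Much of that difference can be measured from data the study already extracts. The pre-interruption segment is also what makes the design an interrupted time series, and the stated arm model does not use it.

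At stake is how usable the between-arm estimate is. The stated purpose of the pilot is a reliable effect size for planning a later trial, and comparing the two delivery modes is an objective in its own right.

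**Working it through.** **The plan's own figures.** Sample Size Justification gives pre/post power only. The arcsine formula for two independent proportions (two-sided 0.05) gives 85.2% for 71% versus 90% with 74 per period, 84.7% for 20% versus 50% with 43, and 80.2% for 53% versus 90% with 21. The plan states 86%, 85% and 80%, so these reproduce to within a point. The infant count also reproduces: 10 PCPs × 6 per month × 9 months = 540 per arm. None of these figures concerns all-in versus add-in.

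**Inputs.** From the documents: 2 clinics and 10 PCPs per arm, 540 infants per arm in each period, documentation 20% before and 50% after. Assumed, because no intraclass correlation is given: logit SDs for clinic (sc), PCP (sp), clinic-by-period (scp) and PCP-by-period (spp). Matching is ignored.

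**Chance baseline gap.** With sc = sp = 0.5, the SD of the difference between the arms' true baseline logits is √[2(0.25/2 + 0.25/10)] = √0.30 = 0.55. The median absolute gap is 0.6745 × 0.55 = 0.37. Multiplying by p(1−p):
- 20%: 0.16 × 0.37 = 6 points; chance of a gap over 10 points 25%
- 71%: 0.206 × 0.37 = 8 points; chance 37%
- 50%: 0.25 × 0.37 = 9 points; chance 46%

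**Standard error of the arm log-odds ratio.** Sampling terms are 2/(540 × 0.25) = 0.0148 (post) and 2/(540 × 0.16) = 0.0231 (pre).
- Post-only variance: V1 = 2[(sc² + scp²)/2 + (sp² + spp²)/10] + 0.0148
- Change from baseline: 2[2scp²/2 + 2spp²/10] + 0.0148 + 0.0231
- Baseline-adjusted: V1 − C²/V0, where C = 2(sc²/2 + sp²/10) and V0 = V1 − 0.0148 + 0.0231

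For SDs of 0.5 with period-specific SDs of 0.2: V1 = 0.348 + 0.0148 = 0.363. The change-score variance is 0.096 + 0.0148 + 0.0231 = 0.134. The adjusted variance is 0.363 − 0.30²/0.371 = 0.120.

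| clinic and PCP SD | period-specific SD | post-only | change score | baseline-adjusted |
|---|---|---|---|---|
| 0.5 | 0.2 | 0.60 | 0.37 | 0.35 |
| 0.5 | 0.3 | 0.65 | 0.50 | 0.46 |
| 0.3 | 0.3 | 0.48 | 0.50 | 0.43 |

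In the first row, with no true arm effect, 95% of estimated odds ratios fall within a factor exp(1.96 × 0.602) = 3.3 of 1 for post-only, and exp(1.96 × 0.347) = 2.0 with baseline adjustment.

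**Second parameterisation.** Take clinic variance s² = ICC/(1 − ICC) × π²/3, 270 infants per clinic and period, and pre/post correlation ρ of clinic effects. At an assumed ICC of 0.05 and ρ = 0.8, s² = 0.173. The SDs are √(0.173 + 0.0148) = 0.43 post-only, √(2 × 0.173 × 0.2 + 0.0148 + 0.0231) = 0.33 for change, and 0.30 adjusted. Over ICC 0.01 to 0.10 and ρ 0.5 to 0.95, adjustment is never worse than post-only. The change score is slightly worse at ρ = 0.5, and at ICC 0.01 with ρ = 0.8 (0.226 versus 0.219, for 20% to 50%).

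**Fewer infants.** The 540 assumes nine post-intervention months, while Duration of Study Participation gives about five months per site; the two need reconciling. With 10 × 6 × 5 = 300 infants per arm and period, the first row becomes 0.61, 0.41 and 0.38, so the conclusion does not depend on this.

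**The case against.** A reader might infer that the arm comparison is biased. It is not: sites are randomised, so a chance baseline gap is sampling error. With a clinic random effect and suitable degrees of freedom, it widens the interval and does not distort it. This stands. What remains is lost precision, and a single realised estimate that carries whatever gap occurred. The clinic effect that would make the interval honest is only optional in the plan.

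A reader might also infer that the plan excludes baseline from every between-arm comparison. The text does not go that far. It gives the unit of analysis as the PCP pre/post and by arm, calls the design an interrupted time series, and lists ANCOVA among methods to be used as appropriate. The accurate statement is that baseline use is not specified. A generic list that names no covariate does not alter the one model that is described.

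Three further points hold in part. Matching on race may remove some imbalance, so the baseline-gap figures may be somewhat high. All SDs are assumed. The adjusted figures also treat the best adjustment coefficient as known; estimating it with four clinics gives back some of the gain.

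Finally, the primary analysis and all the power figures are pre/post, and this is a pilot. That lowers the priority but does not remove the point.

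**Conclusion.** The point holds as a specification gap. The only model stated for all-in versus add-in on penetration uses post-intervention data and names no baseline term, although the data to adjust are already collected. The cost is imprecision: under the assumed SDs of 0.5, a median baseline gap of about 6 to 9 points, and a standard error of 0.60 to 0.65 where 0.35 to 0.50 is attainable. The size of the gain depends on the unstated clinic and PCP variation and on how stable it is across periods; a plain change score can gain nothing. The primary pre/post analysis is unaffected, so this should be fixed but does not threaten the main result. Nor does the change cure having about four clusters: a clinic-level t-test with two clinics per arm has 2 degrees of freedom and a critical value of 4.30.

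**What to change.** Extend, rather than replace, the monthly between-arm model.
- **Baseline.** Fit infants from both periods, or adjust for each clinic's and PCP's pre-period rate. Prefer adjustment, or a model constraining the arms to a common baseline (period and arm-by-period terms, no arm main effect), over a crude change score.
- **Time.** Keep month and phase terms. Components reach the add-in arm at 6-week steps, so a single arm-by-period term would average partial with full toolkit exposure. Each infant's phase is already recorded.
- **Clustering.** Make clinic, PCP, clinic-by-period and PCP-by-period effects mandatory, and name a small-sample method suited to about four clinics.
- **Caregiver knowledge and satisfaction.** Use the retrospective survey as a clinic-level baseline, since the respondents differ between periods. Its different timing is common to both arms.
- **PCP survey.** Adjust self-efficacy and time-cost scores for the pre-roll-out survey where available; PCPs may enrol late, so some will have none. Do not do this for acceptability or use of a component, which have no meaningful value before roll-out.

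The cost is SAP wording and a slightly larger model, which may be harder to fit with so few clinics. No new data are needed.

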Participants will be Nemours primary care offices, Nemours PCPs, and caregivers of children seen for infant primary care well visits at the enrolled office.

Inclusion Criteria:

- Sites: Nemours primary care locations within the Delaware Valley that provide well child care to infants
- PCPs: All Nemours PCPs (physicians and nurse practitioners) at included office locations.
- Caregivers: English speaking caregiver of an infant seen at a participating office location for a well visit before 2 months of age (2 months = 60 days) with an email address available within the EHR.

Exclusion Criteria:

- Caregivers and PCPs: Unable to converse in English.
- Caregivers: Caregivers of infant seen for a first well visit at 61 days of age or older

Subjects that do not meet all of the enrollment criteria may not be enrolled. Any violations of these criteria must be reported in accordance with IRB Policies and Procedures.

STUDY PROCEDURES

Site selection: Emails will be sent to the physician-in-charge of Nemours outpatient office locations within the Delaware Valley with a description of the study and an invitation to participate. For those interested in participating as a site, a REDCap interest survey will be included asking for site specific information (i.e. location, name/contact information of physician-in-charge (PIC), name/contact information of office manager or other person designated by the PIC to handle communication about the trial, Number of PCPs at site). Sites will be matched and paired to create dyads/triads of locations with similar racial demographics of patients (i.e. a dyad with the majority of patients documented as Black or Hispanic, etc). For sites selected for participation in the trial, name/contact information will be collected from the PIC or office manager for all PCPs at the office and anyone else they would like to receive communication about the trial (i.e. nursing staff). An introductory email will be sent to all staff identified by the PIC/office manager explaining the study.

Randomization: Sites will then be randomized within each dyad (i.e. one clinic randomized to the “all-in” arm and the other to the “add-in” arm). All PCPs from the same location will be assigned to the same trial arm.

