compared between two groups. Two sample t-test, Mann-Whitney U-test, Chi-square test, analysis of variance (ANCOVA), liner mixed effects model, logistic regression, and mixed effects logistic regression will be used, for the above comparisons, as appropriate. PCP nested within clinic will be used as the random effects in the model as needed. All tests will be two-tailed with an overall level of significance of 0.05. Benjamini-Hochberg method will be used to adjust the level of significance for multiple comparisons. Statistical software packages SPSS, SAS (version 9.4) or latest version of R will be used for the analysis.

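### All-in versus add-in comparisons may be analysed without clinic, the unit randomised (as few as 2 per arm), so the 0.05 level and the matching interval coverage are not assured

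*Combined protocol and SAP*

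**What the plan says.** In Study Procedures, Site selection: "Sites will be matched and paired to create dyads/triads of locations with similar racial demographics of patients". Under Randomization: "Sites will then be randomized within each dyad", and every PCP at a location takes that location's arm. The section on numbers of sites and subjects requires a minimum of 2 sites and 10 PCPs per arm, and projects 500 caregivers.

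Statistical Methods names the PCP and the trial arm, not the clinic, as the unit of analysis. It assigns a generalized linear mixed model to "compare the proportion of post-intervention documentation and disclosure over time (monthly) between two intervention groups". Acceptability, self-efficacy and time cost are then to be compared between arms, and "Also, dispersion, caregiver knowledge and caregiver satisfaction will be" compared in the same way. The methods offered for these comparisons begin "Two sample t-test, Mann-Whitney U-test, Chi-square test" and, after ANCOVA, continue "liner mixed effects model, logistic regression, and mixed effects logistic regression will be used, for the above comparisons, as appropriate". The next sentence is "PCP nested within clinic will be used as the random effects in the model as needed", followed by "All tests will be two-tailed with an overall level of significance of 0.05" and a Benjamini-Hochberg adjustment.

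No rule says when the random effects are needed. No small-sample method, ICC or use of the dyads in the analysis is given. No confidence level is stated; 95% is implied by the 0.05 level.

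**The concern.** Because a whole clinic receives one arm, any difference between clinics enters the arm contrast directly, and more patients per clinic do not average it out. A t, Mann-Whitney, chi-square or plain logistic test on individuals treats them as independent and leaves that component out of the standard error. A chi-square test of caregiver knowledge by arm would follow the plan to the letter.

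Comparing the two delivery approaches is a stated aim. Sample Size Justification also says the sample will give effect sizes for survey results and documentation in each arm, to inform later trials. Since formal testing is left to those trials, the main harm is false precision: ordinary clinic differences could be read as an arm effect and passed on with intervals that are too narrow.

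**Working it through.** **The plan's own figures.** None is given for the arm contrast. The stated powers (86%, 85%, 80%) are pre/post figures that treat infants as independent. An arcsine calculation gives 85.2%, 84.7% and 80.2%, so they reproduce to within 1 point, but they say nothing about all-in versus add-in.

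**Inputs.** From the documents: 2 clinics and 10 PCPs per arm (minimum), 500 caregivers, two-sided 0.05. Assumed: clinic ICC; correlation r of clinic effects within a dyad (0 if matching does nothing); equal clinics; and half of the caregivers in the post period, because retrospective caregivers are surveyed too. That gives 500/2/4 = 62.5, taken as m = 62 per clinic. With 5 clinics per arm, 250/10 = 25.

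**Formula.** True variance of the arm difference over the variance a naive test assumes:

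V = (1 - ICC) + m × ICC × (1 - r) = 1 + ICC × [m(1 - r) - 1]

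True size = 2 × [1 - Φ(1.96/√V)]; coverage = 1 - size. V exceeds 1 only when r is below 1 - 1/m, which is 0.98 for m = 62 and 0.80 for m = 5.

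**Caregiver outcomes, naive test, 2 clinics per arm, m = 62**

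| r | V at ICC 0.01 / 0.02 / 0.05 | True size | Coverage of a nominal 95% interval |
|---|---|---|---|
| 0 | 1.61 / 2.22 / 4.05 | 12.2 / 18.8 / 33.0% | 88 / 81 / 67% |
| 0.5 | 1.30 / 1.60 / 2.50 | 8.6 / 12.1 / 21.5% | 91 / 88 / 78% |
| 0.8 | 1.11 / 1.23 / 1.57 | 6.3 / 7.7 / 11.8% | 94 / 92 / 88% |

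Binomial simulation (100,000 runs, proportion 0.5) agrees within half a point. With 5 clinics per arm and m = 25, size is 7.8/10.7/18.6% at r=0 and 6.3/7.7/11.8% at r=0.5.

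**PCP scores, t-test, 2 clinics of 5 PCPs per arm** (200,000 simulated runs, ICC 0.01/0.05/0.10): 5.4/7.4/10.0% at r=0, 5.2/6.0/7.3% at r=0.5, and about 5.0-5.6% at r=0.8.

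**Dispersion.** This comes from EHR extraction and its denominator is not given. As an illustration only, 270 per clinic (the 540 infants per arm over 2 clinics) and r=0 would give 31/44/61% at ICC 0.01/0.02/0.05.

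**Penetration.** If PCP is kept but clinic is left out (PCP-mean t-test, 54 infants per PCP, PCP ICC 0.05, r=0), size is about 12/17/27% at clinic ICC 0.01/0.02/0.05. With PCP nested in clinic and a large-sample reference (balanced linear approximation, 30 or 54 infants per PCP, PCP ICC 0.01 or 0.05, clinic ICC 0.01 to 0.05), size is 9-18% with four clinics at r=0 and 6-11% at r=0.5. The four-clinic limit is P(|t| on 2 df > 1.96) = 18.9%. With ten clinics it is 6-8% and 4-5%.

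**Candidate remedies, 2 clinics per arm, m = 62, ICC 0.01 to 0.05.**
- Clinic-level t on 2 df: simulated size 4.8-5.1% at r=0, 3.2-4.0% at r=0.5, 2.5-3.8% at r=0.8.
- Linear mixed model at r=0: 5.5-7.4% with Satterthwaite-type df, and 0-1% with df fixed at 2. The clinic variance is estimated as zero in 21-46% of runs.

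**The case against.** The plan permits a naive test; it does not prescribe one. It names mixed models, states the right nesting, and commits penetration to a mixed model. Its qualifiers can fairly be read as leaving the statistician to choose by outcome type. That stands, so a reader who infers that the arm comparisons will be invalid goes beyond the text. What remains is that nothing fixes the choice in advance, and with four clinics the data cannot settle it, since the clinic variance is often estimated as zero.

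A reader might also infer that any ICC above zero breaks the 5% level unless matching is perfect. The formula shows otherwise: inflation ends at about r = 1 - 1/m, and for PCP scores strong but partial matching nearly removes it. Against that, matching is on racial demographics, and the documents do not show how far this aligns clinics on documentation practice.

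This is a pilot and 2 clinics per arm is a minimum, which lowers the stakes for testing and could reduce the inflation. It does not excuse intervals that are too narrow when reliable effect sizes are the main goal. The Benjamini-Hochberg step means the per-test sizes above are not the final decision rule, but the method takes valid p-values as its input and does not widen intervals.

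**Conclusion.** The point holds for the between-arm comparisons: the plan lists tests that cannot carry a clinic effect and makes clinic optional, so the 0.05 level and the implied 95% coverage are not assured. Under the assumed ICCs, with 2 clinics per arm, naive size for caregiver outcomes runs from 6% (r=0.8, ICC 0.01) to 33% (r=0, ICC 0.05), the latter being the worst corner. For PCP scores it runs from about 5% to 10%. Caregiver outcomes should not be assumed the most exposed: dispersion could be affected as much or more, but cannot be sized from the documents.

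For penetration the gap is narrower, limited to the clinic term and the reference distribution. The documents do not support extending these figures to the pre/post primary comparison, which is made partly within clinics. All sizes rest on the assumed ICC, r, equal clinics and caregiver split. This should be fixed before analysis, chiefly to avoid false precision in the arm contrast passed to later trials.

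**What to change.** In Statistical Methods, for every all-in versus add-in comparison, replace the individual-level tests and the optional random effects with a clinic-level analysis: clinic means or proportions compared using a t reference on (number of clinics minus 2) df. This also works with triads.

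If a mixed model is preferred, including the one for penetration between arms, require the clinic random effect, name the df method, and check its size by simulation at the actual number of clinics. It should not be treated as interchangeable with the clinic-level t when there are 2 clinics per arm.

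State that with about 2 clinics per arm these contrasts are reported as estimates with cluster-aware confidence intervals, not as 5%-level tests. A dyad term is optional; with 2 dyads it leaves 1 df and a critical value of 12.7.

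The change needs no new data. Its cost is width. For a caregiver proportion near 50%, m = 62 and ICC 0.02, the naive half-width is 1.96 × √(0.5/124) = 12.4 points. The clinic-level half-width on 2 df has a simulated median of about 34 points, or 4.303 × √2.22 × 0.0635 = 40.7 at the expected variance. With 5 clinics per arm it is about 17 against 12. The clinic-level t is also somewhat conservative if matching works and the dyad is left out.
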